Psychological Evaluation: The PCL-5 will be conducted at baseline and post study. A Soldier On mental health counselor will be available by phone during the administration of the PCL-5 test in case the test exacerbates any psychological symptoms. Psychological surveys will be entered within one week and monitored for significant increase. If any individuals have a high baseline score for anxiety or depression at study enrollment (as defined in literature) or a > 25% increase over baseline anxiety or depression scores, the participant will be referred for counseling at Soldier On via contacting the individual's Soldier On Case Manager. The case manager will be contacted via a secure email using "SEND SECURE" in the subject line. The email will include the participant's first name and last initial, name of test, normal test parameters, participant's score and comparison to baseline if applicable. Participants with any medical or psychological symptoms that occur during the activities will be referred to clinical services at Soldier On (which has clinical staff) or VA (which is located at same campus as Soldier On) via referral to the case manager. If any participants notify staff of exacerbation of psychological symptoms between activities, they will also be referred to Soldier On/ VA services. If an urgent medical or psychological issue occurs in the field, the study team would call 911 to have them transferred to closest hospital facility. The protocol will be finalized with the study advisory board once convened.

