16. RISKS TO SUBJECTS*

Risks include:

- Potential loss of identifiable data
- Animal bite or scratch
- Exposure to animal disease

INVESTIGATOR STUDY PLAN - REQUIRED

- Exacerbation of psychological symptoms
- Psychological distress due to seeing injured, dying or deceased animals
- Substance abuse exacerbation
- Triggering of psychological symptoms due to unexpected noises in external environment
- Tick bite during outdoor walk
- Allergy exposure
- Sun exposure
- Fatigue/ dehydration during activities
- Traffic accident in route to or from activity
- Contracting Covid-19

Protection against risks

Recruitment and Informed Consent

The PI will meet with each potential participant to review the study including potential risks and benefits. Participants will provide informed voluntary consent.

Participants will be accompanied during activities by the PI, a registered nurse. All wildlife-related activities will be preceded by education and guided by an expert in wildlife care. Risk-specific preventative measures will be taken as below. If any unexpected adverse events occur the event will be given immediate attention at the site (such as first aid if needed) and participant will be referred for appropriate medical or psychological care. The PI will bring a first aid kit and Narcan nasal spray as a precaution for all activities.

All study sites are < 19 miles from a local hospital (ranging from on site to 18.1 miles)

- Soldier On (On campus of VA Hospital in Pittsfield, MA)
- Harvard Forest-Athol Memorial Hospital (4.2 miles)
- Mass Audubon Broad Meadow Brook- UMass Memorial Medical Center (4.9 miles)
- Maine Wildlife Park-Central Maine Medical Center (18.1 miles-highway interstate travel)

Confidentiality: The following steps will be taken to ensure that all patient data remain confidential.

(1) *Use of numeric identifiers:* To ensure confidentiality, study assessments and electronically stored data will be identified only by a unique identifier. The master list linking the patient ID to the patient's identifying information will be maintained in a separate file and will be destroyed at the conclusion of the study. Signed consent forms will be kept in locked filing cabinets and will only be accessible to the PI and staff listed on the IRB approval.

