| ➤ Substance abuse exacerbation (we anticipate some of population will have co-morbidities of substance abuse) | ➤ Inclusion criteria of 30 days or more free of drugs or alcohol abuse and willingness not to use substances before or during activities ➤ Participants will be instructed not to use substances before or during activity trips; if any participants arrive for activity with signs of being under the influence of substances they will be asked to stay home that day; if any participants become impaired due to substance use during activities they will be asked to stay near van under observation of Soldier On project assistant. ➤ If any participants notify staff of exacerbation of psychological symptoms between activities, they will be referred to Soldier On/ VA services via notification of case manager. ➤ If any substance abuse exacerbation occurs during the activities participants will be referred to Soldier On/ VA services via notification of case manager. ➤ If any participant becomes physically or cognitively compromised the PI will call 911 for transport to local ED. ➤ PI will carry Narcan nasal spray in the event of participant overdose; PI will undergo training prior to study implementation |
| ➤ Triggering of psychological symptoms due to unexpected noises in external environment. | ➤ Due to the potential for distant gunfire from a rural gun club or seasonal hunters near the Harvard Forest (as well as a wide range of possible noises in any public environment) we have included that risk in the consent form and added a question to the activity evaluation regarding stress from environmental sounds/ events. Additionally, the PI has contacted the gun club to ascertain that no large scale target shooting events are scheduled during the times when the study activities will take place. |

INVESTIGATOR STUDY PLAN - REQUIRED

| | |
|--|---|
| ➤ Tick bite during outdoor walk | ➤ PI will bring tick spray on all activity trips and will encourage use by each participant ➤ Participants will be instructed to monitor self for tick bites following activity and to call VA MD if any bites occur |
| ➤ Sun exposure | ➤ Although outdoor activities will primarily be in shaded areas PI will provide participants with sunscreen as a precaution |
| ➤ Allergy exposure | ➤ Participants with severe outdoor allergies excluded; participants with mild-moderate allergies encouraged to take medication prior to outdoor activities |

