23. RESOURCES AVAILABLE

Describe study personnel.

Roles

INVESTIGATOR STUDY PLAN - REQUIRED

Principal Investigator

The principal investigator will manage all aspects of the study including IRB approval. This includes:

- Oversee the conduct of all facets of this study, including human subjects review, communication with team members, collaboration with community wildlife facilities, research-related activities; personal oversight of intervention activities, budget; compliance and scientific integrity;
- Be responsible for the IRB submission and overseeing human subjects procedures of all participants enrolled in the study;
- Conduct training of personnel and ensure that personnel have taken courses in Good Clinical Practice and CITI training
- Ensure that research personnel have training in all study-related procedures and standards to ensure intervention fidelity procedures are maintained.
- Meet with individuals recruited by Soldier On Research Assistant to screen for study eligibility and enroll as study participants
- Conduct baseline study measures
- Schedule intervention activities in collaboration with Soldier On and community facilities
- Refine animal-assisted activities in collaboration with Advisory Committee
- Accompany study participants during activities at community wildlife facilities
- Conduct all study measures pre and post activities
- Oversee data collection, data management and quality control with particular emphasis on data accuracy; including working with study statistician to structure the primary datasets, data linking procedures, codebook development and data documentation and security procedures.
- Perform qualitative data analysis
- Responsible for execution (along with Co-I) of the data safety monitoring plan.
- Work with the research team to prepare manuscripts, coordinate study results dissemination activities and prepare R01 for the full scale study.
- **Co-Investigator** Provide ongoing advisement to the research team as a senior scientist;
- Assist with analysis and interpretation of the data
- Serve as Safety Officer which will include reviewing monthly safety report with PI
- Consult on abstracts and manuscripts developed from the study and development of plan for future R01.
- **Co-Investigator** Design the final intervention study analysis plan in consultation with PI and other Co-I
- Be responsible for ensuring that the statistical design is implemented according to plan;

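### A participant impaired during an outing waits near the van with an observer who is given neither Narcan nor Narcan training, and no step is written for alerting the PI

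*Combined protocol and SAP*

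**What the plan says.** The substance-abuse row of the risk table in section 16 states that some participants are expected to have substance-use comorbidity. It sets out several responses. Someone who arrives apparently under the influence is asked to stay home. If, later on, any participants "become impaired due to substance use during activities they will be asked to stay near van under observation of Soldier On project assistant". The same row adds: "If any participant becomes physically or cognitively compromised the PI will call 911 for transport to local ED". On overdose it says: "PI will carry Narcan nasal spray in the event of participant overdose; PI will undergo training prior to study implementation".

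The text above the table, under Protection against risks, says: "Participants will be accompanied during activities by the PI, a registered nurse". It also says: "The PI will bring a first aid kit and Narcan nasal spray as a precaution for all activities". It promises prompt attention on site for unexpected adverse events, without naming who gives it. Section 14 adds that for an urgent medical or psychological problem in the field "the study team would call 911 to have them transferred to closest hospital facility".

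On training, the staff-training paragraph in section 16 (repeated in section 26) gives all project staff CITI certification and confidentiality training, and gives the project assistant training in recruitment and assessment. Section 23 gives the PI a general duty: "Ensure that research personnel have training in all study-related procedures and standards to ensure intervention fidelity procedures are maintained".

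**The concern.** The plan divides two things between two people. Watching the impaired participant falls to the project assistant at the van. Narcan and the training to use it belong to the PI, whose written duties in section 23 are to accompany participants at the facilities and to conduct the pre- and post-activity measures. If the group carries on while one person waits at the van, the antidote may be with the group and not with the person being watched for substance effects. At stake is how quickly Narcan could be given if that impairment turned out to be an overdose that Narcan can treat. This is a participant-safety matter only.

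**Working it through.** The plan gives no figure on this point, so the check is a reading of every place that deals with Narcan, the observer, the PI's whereabouts, training or emergency response.

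| Question | What the document states | Where |
|---|---|---|
| Who watches the impaired participant? | Soldier On project assistant, near the van | Section 16, risk table |
| Who has Narcan? | The PI, in both mentions | Section 16, text and risk table |
| Who is trained in it? | The PI | Section 16, risk table |
| What is the project assistant trained in? | Recruitment and assessment, plus the CITI and confidentiality training given to all staff | Section 16, staff training; section 26 |
| Who calls 911? | The PI in the substance row; the study team for urgent field problems | Section 16; section 14 |
| Where is the PI? | On the outing, accompanying participants | Sections 14, 16, 23 |
| Does the observer alert the PI? | Not stated | None found |
| Does the PI assess this participant? | Not stated; ongoing PI assessment is listed only in the row on psychological symptoms | Section 16, risk table |
| Is Narcan left with the observer? | Not stated | None found |

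Three steps follow.

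1. *Named holders.* One person is named as carrying Narcan, the PI. The person named as observer is someone else and is assigned none.
2. *Whether the two can be apart.* The van rule takes the participant out of the activity, while the PI's stated duties follow the activity. Groups have up to 10 participants (section 11), and eligibility requires being able to cover up to a mile (section 6). Seven of the eight sessions list a drive: two each at the forest, the wildlife center and the wildlife park, and one at Mass Audubon (2 + 2 + 2 + 1 = 7). The eighth is at Soldier On. No distance between the van and the group is given, so separation is possible on the text but cannot be measured.
3. *Whether another provision closes the gap.* The 911 rule in the substance row implies that the PI learns of the problem, but no step for telling the PI is written. Its trigger, being physically or cognitively compromised, also overlaps with being impaired, so staff cannot easily tell which instruction applies. The section 23 training duty is tied to intervention fidelity and does not mention Narcan. None of these puts Narcan at the van.

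On job titles: section 23 describes the Soldier On hire as a research assistant, and the document does not say whether this is the same person as the project assistant. The conclusion does not depend on it, because neither title is given Narcan or overdose training.

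**The case against.** The strongest reply is that this argues from silence. The row can be read as a graded response: impairment leads to observation, a compromised state leads the PI to call 911, and overdose leads the PI to use Narcan. On that reading the PI is presumed to be informed and close by, and what is missing is only a hand-off sentence. Much of this stands. A reader might infer that the plan has no medical response, or that it sends the participant away from help. The document supports neither: a nurse is on the outing, the study team can call 911, and the text allows separation without requiring it.

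A reader might also infer that the person at the van is the one likeliest to overdose. That is not supported either. Impairment covers alcohol as well as drugs, opioids are not named, and no rate is given. The 30-day criterion, the stay-home rule and the power in section 15 to withdraw an intoxicated participant all reduce exposure.

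Finally, this may be settled elsewhere. Section 14 refers to a separate data and safety monitoring plan, which was not available, and says: "The protocol will be finalized with the study advisory board once convened". That limits the point to the document in hand.

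What the reply does not answer is the stated allocation itself. The plan chose to carry Narcan in addition to 911, and then named an observer who does not have it.

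**Conclusion.** The point holds as an inexpensive improvement to consider. As written, the plan permits an impaired participant to be watched by someone without Narcan or stated overdose training, apart from the only named supply, with no written instruction to alert the PI. Its size cannot be put in numbers: the document gives no impairment rate, overdose rate, distance or response time, and the screening rules suggest that the event would be uncommon. Sample size, error rates and outcomes are untouched. The conclusion assumes that neither the monitoring plan nor the advisory-board revision already supplies the missing step.

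**What to change.** Amend the van line in the section 16 risk table along these lines: *If a participant appears impaired during an activity, the project assistant alerts the PI (RN) at once and the PI assesses the participant. If the participant then waits near the van, the observing assistant carries a second Narcan kit and has completed the same Narcan training as the PI.* Amend the Narcan sentence under Protection against risks to match. The PI's own kit stays with the group. No new 911 authority is needed, since section 14 already gives it to the study team.

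The cost is one extra kit, a short training for existing staff and an IRB wording amendment. The benefit is confined to outings still to come. Section 9 puts the study in a no-cost extension until December 2022 and does not show how many outings remain. If the monitoring plan already covers the hand-off, a cross-reference in the risk table is enough.

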17. POTENTIAL DIRECT BENEFITS TO SUBJECTS*

We anticipate that the activities in this study will be enjoyable to participants given data from the PIs prior studies at two of the locations. Additionally, participants may receive benefits through improvements to psychological and/or physical well-being. Moreover, we hope that the provision of the bird feeders and education might provide sustainable benefits in the future beyond study conclusion. Participants will also be provided with a journal for personal use if they would like to document future experiences observing wildlife.

18. VULNERABLE POPULATIONS*

- a. No inducements, monetary or otherwise, will be offered to terminate a pregnancy
- b. Individuals engaged in the research will have no part in any decisions as to the timing, method, or procedures used to terminate a pregnancy
- c. Individuals engaged in the research will have no part in determining the viability of a neonate

19. MULTI-SITE RESEARCH*

N/A

20. COMMUNITY-BASED PARTICIPATORY RESEARCH*

N/A

INVESTIGATOR STUDY PLAN - REQUIRED

21. SHARING OF RESEARCH RESULTS WITH SUBJECTS*

A presentation of the results will be provided on site at Soldier On following the conclusion of the study. Soldier On will also be provided with a copy of any publications that result from the study. Participants will have the opportunity to provide their contact information to the research team during intake if they want to be notified about results in future.

22. SETTING

We will partner with a successful veteran's organization, an internationally-renowned forest facility and three wildlife facilities that have expert staff well versed in helping the public to experience wildlife safely. Two of these (New England Wildlife Center and Maine Wildlife Park) have been sites for the PI's prior study. Letters of support have been written by all these facilities.

-Soldier On: This private non-profit organization provides housing and support services to veterans (currently approximately 600 veterans served) and UMASS Chan Medical School faculty have been partnering with them on research for the past 10 years. They have a nationally known model of sustainable affordable housing for veterans. Veterans will be recruited through Soldier On. Soldier On has multiple vehicles and drivers and has agreed to transport the veteran participants to the wildlife activity sites.^{25, 26}

-Harvard Forest: This 4,000 acre forest of Harvard University was founded in 1907. The Forest is a Long-Term Ecological Research Site, funded by the NSF for research into forest dynamics. It has multiple walking/hiking trails including accessible trails. (Petersham, MA)²⁷

-New England Wildlife Center: The NEWC provides veterinary care to orphaned and injured wildlife. The Center integrates care with teaching to share skills and knowledge with people of all ages. NEWC staff are experienced with integrating novices into animal care including a highly successful animal care program for inmates. (South Weymouth, MA)²⁸

-Maine Wildlife Park: The MWP is a wildlife education center on 40 acres operated by the Maine Dept. of Inland Fisheries and Wildlife. The park has 100 animals (30 species) of native Maine wildlife living in a sanctuary setting. (Gray, ME)²⁹

-Mass Audubon Broad Meadow Brook Conservation Center and Wildlife Sanctuary: This center is the largest urban wildlife sanctuary in New England with over 400 acres including educational facilities and a universally accessible sensory trail. (Worcester, MA)³⁰

Privacy

- When recording heart rate the participants will be given a card and asked to record their heart rate by looking at their wrist monitor. Data will be written rather than spoken aloud.
- The focus groups will be held in a private room at Soldier On.
- We will schedule the interviews/ phone calls so that participants can plan in advance to be in a private space.

23. RESOURCES AVAILABLE

Describe study personnel.

Roles

INVESTIGATOR STUDY PLAN - REQUIRED

Principal Investigator

The principal investigator will manage all aspects of the study including IRB approval. This includes:

- Oversee the conduct of all facets of this study, including human subjects review, communication with team members, collaboration with community wildlife facilities, research-related activities; personal oversight of intervention activities, budget; compliance and scientific integrity;
- Be responsible for the IRB submission and overseeing human subjects procedures of all participants enrolled in the study;
- Conduct training of personnel and ensure that personnel have taken courses in Good Clinical Practice and CITI training
- Ensure that research personnel have training in all study-related procedures and standards to ensure intervention fidelity procedures are maintained.
- Meet with individuals recruited by Soldier On Research Assistant to screen for study eligibility and enroll as study participants
- Conduct baseline study measures
- Schedule intervention activities in collaboration with Soldier On and community facilities
- Refine animal-assisted activities in collaboration with Advisory Committee
- Accompany study participants during activities at community wildlife facilities
- Conduct all study measures pre and post activities
- Oversee data collection, data management and quality control with particular emphasis on data accuracy; including working with study statistician to structure the primary datasets, data linking procedures, codebook development and data documentation and security procedures.
- Perform qualitative data analysis
- Responsible for execution (along with Co-I) of the data safety monitoring plan.
- Work with the research team to prepare manuscripts, coordinate study results dissemination activities and prepare R01 for the full scale study.
- **Co-Investigator** Provide ongoing advisement to the research team as a senior scientist;
- Assist with analysis and interpretation of the data
- Serve as Safety Officer which will include reviewing monthly safety report with PI
- Consult on abstracts and manuscripts developed from the study and development of plan for future R01.
- **Co-Investigator** Design the final intervention study analysis plan in consultation with PI and other Co-I
- Be responsible for ensuring that the statistical design is implemented according to plan;
- Be responsible for the statistical integrity of the intervention study;
- Assist with execution of the data safety monitoring plan;
- Conduct, report and write up of final feasibility study analyses;
- Consult on abstracts and manuscripts developed from the study and development of statistical analysis plan for future R01.

INVESTIGATOR STUDY PLAN - REQUIRED

Research Assistant (UMass Chan Medical School)

A research assistant will be hired to assist with study logistics, data collection and data entry. The research assistant will undergo CITI training and will report directly to [name].

Community Partner (subcontract)

Soldier On is a private non-profit organization that provides housing and support services to veterans. One of the co-investigators has a strong working relationship with Soldier On from prior research. Veterans will be recruited through Soldier On for the study. Soldier On will undertake the following:

- Appoint a site advisor to serve as lead representative of Soldier On in this study. Hire a research assistant to recruit participants for the study and assist with activity logistics. The research assistant will be CITI trained and listed as study staff.
- Provide transportation to study activities using Soldier On vehicles and drivers

Consultants

We will have three expert consultants, one representing each of the facility settings where animal-assisted intervention will take place. Of note is that the PI has worked extensively with two of the consultants, in her previous study.

Advisory Committee: We will convene an advisory committee to inform refinement and logistics of the intervention protocol prior to start of study, after year 1 and after study conclusion. Initial meetings will be held individually in order to focus on unique aspects of each site.

The role of the consultants is primarily to advise and assist with the study intervention rather than the research. Two of the consultants and possibly the third will likely be providing facility orientation and possibly some education for the participants as they are part of the staff at the facilities. They will not have access to identifiable research information or data. The lead person at Soldier On may have awareness of who are study participants and may be asked to assist with referrals for medical or psychiatric care if needed. This person will undergo CITI training. Other members of the advisory committee will be providing feedback on the study planning/logistics only.

